#### **E4c. Actigraphy Device**

Participants will be warned about possible irritation to the skin and general discomfort wearing the device during the informed consent session. If the participant says they cannot wear the ActiGraph due to skin irritation, researchers will provide the participant with a more comfortable way of wearing the ActiGraph on the wrist (e.g., using a softer material on the wrist strip).

#### **E4d. Privacy and Confidentiality**

We will take multiple steps to protect participants' privacy and confidentiality. All of the data collected from participants will be kept in strict confidence. No information that is linked to a research participant's identity will be provided to anyone outside of the study or regulatory entities responsible for oversight without permission from the participant.

#### **Electronic Data**

All study data collected for purposes of data analysis will be de-identified, labeled with a code number that is unique to each research participant, and maintained separate from any identifying information.

All electronic data collected via telephone, online, and Ecological Momentary Assessment (EMA) data will be encrypted and stored in a HIPAA- and IRB-compliant web-based system. These data will also be downloaded and saved in a limited access folder on the secure UW network drive.

The participant will send back the ActiGraph to study personnel in a provided self-addressed stamped envelope at the end of the 4-Week Post-Treatment Monitoring Period. Study personnel will download the data collected by the ActiGraph and link it to the participant's other data via their participant identification number. The data will be stored in the same limited access folder on the secure UW network drive as the other data used for data analysis purposes. Data may be downloaded from the ActiGraph only with the assistance of ActiGraph software that is

unavailable to the general population. That is, participants will NOT have the ability to download the data from the device itself (e.g., onto their personal computer).

An electronic Master List key code will be maintained that links the participants with their code number. This key code will be stored in a password-protected Microsoft Access database that does not contain any study data. This database will also reside in a limited access folder on the UW network drive. Only approved study personnel will have access to the Master List key code, participant identifying information, and de-identified study data. We will analyze and report participant data in aggregate form and no PHI will be entered into these analyses or reports.

One exception to the protocol of separating all study data from participant identifying information pertains to audio recordings generated for each treatment session. Specifically, the group treatment sessions will be audio recorded to make sure study clinicians are following study procedures. The study clinicians will notify participants before the start of the session that they will be recording the session. The recordings will be stored in a limited access folder on the secure UW network drive. Audio recordings will be (1) reviewed by study personnel and used for assessing fidelity to treatment protocol by study clinicians, and (2) used for training purposes. The audio recordings will not be labeled with any participant identifying information. The only identifying information that will be contained in the recordings will be participants' voices and if the study clinician or group members state participants' names during the discussion.

Another exception pertains to the audio recorded qualitative interviews collected after the conclusion of treatment. Specifically, unblinded research staff will use open-ended questions to interview participants about their experiences in the treatment program and collect study feedback, if any. Effective 2020, there will also be a question on COVID-19's impact during treatment. Research staff will notify participants before the start of the interview that they will be recording the interview. The recordings will be stored in a limited access folder on the secure UW network drive. Audio recordings will be transcribed (by third party software) and reviewed by unblinded study personnel only and coded for themes that may highlight information about the program not captured by study outcome data. The audio recordings will not be labeled with any participant identifying information. The only identifying information that will be contained in the recordings will be the participant's voice and if the staff member states the participant's name during the interview. No blinded staff members will have access to these qualitative interviews.

Additionally, another exception is the alerts sent to participants to complete the EMA surveys via notifications and/or email messages. Specifically, the alert may include the participant's identification number in the body of the notification/email, creating a crosswalk between the participant's identity and participant data. Please note, however, that the EMA data that will be collected will not be stored with any identifying information.

Finally, participants will be asked to complete a document outlining home practice completion. The document itself will not contain any identifying information, but since it will be on Google Drive, identifying information may be included (e.g., name or participant ID). The documents will then be downloaded from Google Drive and engagement in home practice data will be extracted and stored. The documents will be stored in a limited access folder on the secure UW network drive only accessible by unblinded research staff.

## **Hard Copy Data**

Any hard copies of study forms will be stored on a secure, badge-protected floor in the Ninth and Jefferson Building. Any hard copy forms containing participant identifiers will be stored in locked filing cabinets in a locked cabinet separate from the de-identified study data.

#### **E4e. Mental Health Issues / Suicidality**

Although the study poses no serious risks to participants, participants may notify research personnel about pre-existing mental health issues that have not been previously identified. A suicide risk assessment protocol will be implemented by non-clinical staff (see below). It should be noted that risk of suicide is an exclusion criteria for this study, so we anticipate that the likelihood of suicide risk is low.

##### **Suicide Risk Assessment Protocol: Non-Clinical Research Staff**

A suicide risk assessment protocol will be implemented by non-clinical staff under the following condition:

*If a participant mentions or alludes to thoughts, intentions, plans or behaviors related to self-directed violence (SDV) outside of the context of formal assessment.*

Study staff (e.g., Research Coordinator, Research Assistant) are not licensed mental health providers. This protocol outlines specific steps that study staff will follow in order to ascertain whether a study investigator or study clinician who is supervised by a licensed mental health care provider needs to be contacted for follow-up assessment and/or triage. In the event that a study staff member perceives sufficient risk that further assessment is warranted, the study staff will alert an investigator or a study clinician who can assess risk. Because our research staff are not clinicians (i.e., they have no official clinical role), our plan primarily reflects the importance of *activating the procedures for suicide risk assessment and risk management/suicide prevention.*

Thus, in the event that the participant mentions thoughts, intentions, or plans related to harm to self, the research staff member will ask the participant some clarifying questions, such as: "Let me clarify, are you having any thoughts about harming yourself deliberately, or are you just thinking about dying or that you would be better off dead?" or "Let me clarify, are you having any thoughts about deliberately harming yourself?" If the participant endorses follow-up questions that suggest a possibility of risk for suicide, the research staff member will gather additional information about acute risk (i.e., presence of intent, plan, means for self-directed violence, protective factors such as presence of dependents).

In the course of this discussion, if the participant clarifies that while they are having thoughts about self-harm, they have no intent or plan, and if they volunteer reasons they would not harm themselves (e.g., having dependents, or religious beliefs that prevent suicide), then this will be considered a negative screen. Because suicide risk assessment for clinician is beyond the role of non-clinical research staff members, we propose a low threshold for a positive screen.

1. In the event of a negative screen, the research staff member will complete the interaction with the participant, and then alert [name], [name], or a study clinician within 24 hours to review the screen and determine if further action needs to be taken.
2. In the event of a positive screen over the telephone during an assessment (i.e., if the research staff member perceives that there is imminent risk of self-harm because the

participant has expressed information about intent, means, plans for self-harm) then the research staff member will:

- a. Verify the contact information and location of the participant and thank them for their candor and advise the participant that they will be contacting a mental health provider to perform a further assessment. They will use the following script: "Thank you for being honest with your answer(s). To ensure that you are safe and getting any help you might need I am going to ask a mental health provider to speak with you more about this." The research staff member will keep the participant on the phone while using another modality of communication (i.e., text, e-mail, pager) to reach [name], [name], or a study clinician who is supervised by [name] or [name] (who are both licensed, privileged, and credentialed) to do more in-depth assessment of risk.
- b. Once a clinician contacts the participant they will follow best clinical practice for the assessment and management of suicide risk (see "Suicide Risk Reduction Protocol – Clinical Staff" below).
- c. If a clinician is not available immediately and/or if the research staff member perceives imminent risk, they will encourage the participant to seek immediate evaluation at the nearest ER and/or to contact the National Suicide Prevention Lifeline (<https://suicidepreventionlifeline.org/>).
- d. After directing the participant to the crisis line or ER, the research staff member will follow-up with [name] or [name] to determine if additional steps (e.g., calling 911) need to be taken. A study clinician will follow up with the participant within 24 hours.
- e. [name], [name], or a study clinician who is supervised by a licensed health care provider will document actions taken. An AE report will also be filed if indicated.

3. In the event that a study staff member has reason to believe a participant is in grave danger (as would be the case extremely rarely, and only if they made explicit statements to this effect):
  - a. The staff member could contact local police and request a well-being check.

#### **Suicide Risk Assessment Protocol: Clinical Research Staff**

The goal of this protocol is to ensure that reasonable steps are consistently taken by study clinicians and investigators to protect participant safety and welfare. The study clinicians will be credentialed and privileged providers at the UW or Masters-level or post-doctoral level clinicians under the supervision of a credentialed and privileged UW provider. Additionally, both [name] and [name] are credentialed, privileged, and licensed providers at the UW. Should there be any indication of risk for self-directed violence that arise during interactions with study staff, the study clinicians/investigators will follow the same specific procedures and policies that psychologists who are clinicians at UW follow for assessing and managing risk.

In instances where the clinician is concerned about safety/suicide risk in a study participant (i.e., if they state or allude to thoughts or plans of self-directed violence, mention recent self-directed violent behavior or behavior preparatory to self-directed violence during a study intervention session), or in instances where a study clinician/investigator is contacted by a

research staff member and asked to follow-up with a participant, the study clinicians/investigators will follow the same risk assessment and prevention protocol that is required of UW licensed psychologists.

## **F. Data Safety Monitoring**

### **F1. Adverse Event & Unanticipated Problems Definitions**

#### **F1a. Adverse Event (AE)**

An adverse event (AE) is any untoward medical occurrence in a participant during participation in the clinical study or with use of the experimental agent being studied. An adverse finding can include a sign, symptom, abnormal assessment (laboratory test value, vital signs, electrocardiogram finding, etc.), or any combination of these regardless of relationship to participation in the study. Staff will document any occurrence that meets this definition, is a new symptom/condition for the participant, and results in either self-treatment or treatment by a health care provider.

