Second, clinicians will employ several protective measures when administering the treatment interventions. As it relates to the activation skills intervention, at the first treatment session clinicians will get to know the personal physical capabilities of each participant, allowing any future physical activity recommendations to be tailored to the individual. Further, before participants complete any assigned physical activities, the clinician will review the activity with the participant to ensure that it is reasonable and safe. Lastly, the clinician will routinely assess during the treatment phase whether participants are experiencing any adverse effects related to the activity skills intervention, and will (in conjunction with the study medical doctor, if needed) advise the participant whether they should stop or modify their activity, or recommend they seek guidance from their primary health care provider (if the event is significant but non-imminent) or urgent/emergency care (if the event is life-threatening or an urgent, acute medical issue). As it relates to the cognitive therapy and mindfulness meditation interventions, during each treatment session clinicians will routinely assess whether participants are experiencing any adverse effects related to the treatment interventions, and will (in conjunction with PI supervision, if needed) advise the participant whether they should stop or modify participation in mindfulness meditation or cognitive therapy treatment activities.

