### **F2c. Severity of Event**

The following scale will be used to grade adverse events:

1. Mild: no intervention required; no impact on activities of daily living (ADL)
2. Moderate: minimal, local, or non-invasive intervention indicated; moderate impact on ADL
3. Severe: significant symptoms requiring invasive intervention; participant seeks medical attention, needs major assistance with ADL
4. Life-threatening: the event is potentially fatal

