### **F3. Reporting Procedures**

#### **F3a. Regulatory Event Documentation**

All regulatory events, incidents, or problems involving risks to participants, including AEs, SAEs, and Unanticipated Problems (UP), will be documented in the REDCap electronic database that houses all study data. All regulatory events will share a common electronic form template. Two separate copies of the same form will exist, (1) one for events involving information that could unblind staff to a participant's treatment allocation, and (2) another for events without details that could unblind staff to a participant's treatment allocation. Only unblinded staff will have access to the form that outlines events with details that could unblind staff to a participant's treatment intervention. The form will be filled out for every regulatory event. A study clinician will review all events that are designated AEs or SAEs to assess severity and relationship to study procedures.

The Regulatory Event form will assess the following information for all three event types (AE, SAE, and UP):

- A brief description of the incident/problem.
- Dates corresponding to event onset, stop, and location.
- Whether or not the event was unexpected or unanticipated.
- Whether or not the event placed participants or others at greater risk of harm than was previously recognized.
- The degree to which the event was related to study procedures.
- Whether or not the study procedures were discontinued due to the event.
- The steps taken to remedy the event.
- The steps taken to report the event to the appropriate entities.
- (AE/SAE only) A ranking of the severity of the event according to section F2c.
- (AE/SAE only) The specific outcome of the event.
- (SAE only) The category of the SAE.

For reporting purposes, regulatory event documentation will be aggregated into central reports using REDCap's "Reports" functionality. The "Reports" functionality allows data to be pulled from the Regulatory Event forms and summarized in one central report. The content of these reports and the frequency in which they are distributed to regulatory bodies is outlined in sections F3b. and F3c.

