##### **Treatment**

Study clinicians will collect unsolicited information reported by participants during treatment sessions including, but not limited to, physical or psychological decline, or unexpected reactions to the treatment intervention.

Any AEs collected during treatment sessions will be recorded on the participant's REDCap Regulatory Events form created and completed during participation.

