### **Annual Report**

Study staff will generate an Annual Report during the last quarter of the year. The structure of the annual report will be identical to the three quarterly reports done earlier in the year; that is, it will follow the Study Report Outline (see below) with a general summary of what has occurred over the past year and most recent updates and progress since the third quarterly report. It will also include a list and summary of any protocol deviation or violation that warrants a note-to-file, and AEs, SAEs, and unanticipated problems; anything already reviewed in previous quarters by the DSMC Chair and Co-PIs will be clearly indicated in the report. In addition, the Annual Report will address (1) whether AE rates are consistent with pre-study assumptions; (2) reason for dropouts from the study; (3) whether all participants met entry criteria; (4) whether continuation of the study is justified on the basis that additional data are needed to accomplish the stated aims of the study; and (5) conditions whereby the study might be terminated prematurely. The Annual Report will be sent to all members of the DSMC. The DSMC along with the co-PIs will convene to review and discuss the report. The annual progress report will be forwarded to (1) the UW IRB and (2) NCCIH.

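### F1a documents an adverse event only if it is both new and treated, so untreated mild events and non-serious worsening of existing symptoms drop out of the AE counts

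*Protocol*

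**What the plan says.** Protocol F1a opens broadly: "An adverse event (AE) is any untoward medical occurrence in a participant during participation in the clinical study", whatever its relation to the study. The last sentence of the same paragraph narrows what staff write down. The occurrence must meet the definition and must also be one that "is a new symptom/condition for the participant, and results in either self-treatment or treatment by a health care provider".

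F2c sets the lowest severity grade as "Mild: no intervention required; no impact on activities of daily living (ADL".

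F3a has no condition of novelty or treatment: "All regulatory events, incidents, or problems involving risks to participants, including AEs, SAEs, and Unanticipated Problems (UP), will be documented".

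F4g, under Treatment, says "Study clinicians will collect unsolicited information reported by participants during treatment sessions", with examples that include "physical or psychological decline, or unexpected reactions to the treatment intervention". Under General it adds suicidal thoughts, greater use of alcohol or drugs, and psychological decline. In both places, only what counts as an AE goes on to the Regulatory Events form.

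E4b describes an active enquiry. For CT and MM, "during each treatment session clinicians will routinely assess whether participants are experiencing any adverse effects related to the treatment interventions". For AS, the clinician asks routinely during the treatment phase. E4b does not say how the answers are recorded.

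Under F3b, AE summaries go each quarter to the DSMC, the IRB and the funder. The Annual Report must address "whether AE rates are consistent with pre-study assumptions".

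**The concern.** A severity scale that starts at events needing no intervention is of little use if an untreated event is never written down. Participants all enter with chronic pain and opioid use (D5), so a pain flare or a rise in opioid use is in general a change in something already present, not a new condition. The rule therefore bears on the harms that these three treatments would most plausibly cause. At stake is whether a low AE count in the safety reports means few harms or a narrow recording rule.

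**Working it through.** No arithmetic applies beyond counting cases. The check sets the rules side by side.

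**1. What F1a lets through.** Take a non-serious occurrence that meets the AE definition and apply the two further conditions.

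| Occurrence | New | Treated | Documented as an AE under F1a |
|---|---|---|---|
| New symptom, self-treated or treated by a provider | yes | yes | yes |
| New symptom, untreated | yes | no | no |
| Existing symptom made worse, treated | no | yes | no |
| Existing symptom made worse, untreated | no | no | no |

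One of the four cells passes. This counts kinds of event and is not a share of events.

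**2. Against the F2c grades.** Mild means that no intervention was required. F1a asks whether treatment took place. A new mild symptom that the participant chose to self-treat passes and can be graded Mild. An untreated one is never documented, so it cannot be graded. The Mild grade is largely, not wholly, emptied.

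**3. Against the expected harms.** E3a and E3b anticipate a short-lived rise in pain, mild anxiety, frustration or stress, distress from memories, brief disorientation or drowsiness with MM, and strain or injury with AS. A rise in pain fails the novelty condition. Brief drowsiness or stress will usually go untreated. Strain or injury in AS would normally be new and often treated, so it would usually pass.

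**4. Other routes into the safety record.**
- *SAE (F1c):* no novelty or treatment condition, so worsening that leads, for example, to hospitalization is caught. It covers serious events only.
- *Unanticipated problem (F1b):* all three criteria must hold, one being that the event is unexpected. Risks already listed in E3 will in general not meet it unless their severity or frequency is unexpected.
- *F4g:* decline and increased substance use are to be collected, but only AEs reach the form, which leads back to F1a. Whether untreated or non-new decline is logged is therefore unclear.
- *Outcome data (D6g, Table 3):* pain intensity, depression, anxiety and medication use are measured weekly from baseline through post-treatment monitoring. No section makes a worse score an AE. The Study Report Outline limits tables to aggregate baseline and safety data, so outcome worsening does not reach the monitor by that path.
- *Chart review:* F4g says that charts will not be monitored for AEs.

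**5. Solicited or unsolicited.** E4b has clinicians ask. F4g describes session information as unsolicited. The revision history suggests why: Section F was revised in version 2.2 (June 1, 2021), and the E4b enquiry was added in versions 2.21 and 2.3 (June 24 and July 14, 2021). The current text of the two sections still has to agree.

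**The case against.** The strongest reply is that little is lost. Pain, mood and opioid dose are measured repeatedly, and opioid dose is the primary outcome. Serious events are reported without the filter. F4g names physical and psychological decline, and F3a requires a form for every regulatory event. The protocol regards the treatments as carrying minimal risk, so a narrower AE scope can be defended, and Section F was aligned with a separate monitoring plan that is not among these documents. E4b already asks for routine enquiry in all three arms. Finally, if every worsening counted, twice-daily surveys in people with fluctuating pain could generate a flood of AE forms.

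Much of this stands, and it rules out several stronger readings that a reader might infer:
- *All worsening of pain or distress goes unrecorded.* It does not: serious worsening is an SAE, and scores are kept as study data. Distress is not an entry criterion, so first-onset anxiety or low mood can be new.
- *No Mild event is ever captured.* A new, self-treated one is.
- *The filter feeds a stopping threshold.* F4e is a matter of judgment and contains no AE rate.
- *The three treatments will be shown to look safer by some known amount, or relative to one another.* The pre-study assumptions are not given, safety tables are aggregate, and the SAP text describes no AE comparison.

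The reply does not close the gap. Outcome scores do not trigger AE forms, the F4g and F3a routes return to the F1a rule, and a deliberate narrow scope would still conflict with the definition and the grade beside it. The worry about form volume is a reason to set a boundary, which the fix does.

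**Conclusion.** The point holds in a limited form. F1a's documentation rule is inconsistent with its own definition, the Mild grade in F2c, F3a and the F4g list. Followed as written, it leaves out untreated mild events and non-serious worsening of pre-existing symptoms, which include harms that E3a and E3b expect. AE counts in the quarterly and annual reviews are therefore too low for these kinds of event. The direction is clear. The amount is not, because the documents give neither observed nor assumed AE rates. The conclusion assumes that staff apply F1a literally and that the monitoring plan, which is not available here, does not override it. It should be changed, but it does not threaten the primary analysis.

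**What to change.** - **F1a:** document any new or worsened untoward occurrence that a participant reports to staff or that the E4b enquiry elicits, whether or not it was treated. Grade it by F2c and flag treatment in a separate field. State that routine fluctuation in EMA or weekly scores alone is not an AE.
- **F4g and E4b:** replace the description of session information as unsolicited. Use the same enquiry at each session in all three arms, and record the answers on the Regulatory Event form.
- **If data collection is complete** (the SAP is written in the past tense): report the AE counts with the F1a rule stated beside them, so that low counts are not read as absence of mild harm or worsening.

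The cost is protocol wording, one extra field and more AE forms for mild events. Limiting the rule to reported or elicited events keeps that number manageable.
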